8.0 DATA MANAGEMENT

8.1. Data Handling and Statistical Considerations:

8.1.1. The same protocols and procedures for data quality and control that are readily used for prior studies conducted with the Geriatric Oncology Research Group and currently being overseen by our office. Data will be entered into REDCap (see section 8.3.5 below).

8.1.2. After entering into REDCap, data are audited visually for errors. R, SPSS and SAS will be used for the statistical analyses. Unless otherwise stated, all statistical tests will be performed at the two-tailed 5% level of significance. Likewise, 95% confidence intervals will be constructed for the estimation of effects.

8.1.3. The assumptions underlying all statistical analyses will be thoroughly checked using appropriate graphical and numerical methods.^{70,71} In case of violations of distribution assumptions such as normality, appropriate nonparametric methods will be attempted.^{72,73} If outliers or influential data are detected, the accuracy of the data will be investigated. If no errors are found, analyses may be repeated after

removing these cases to evaluate their impact on the results. However, the final analyses will include these data points.

8.2. Data Analysis and Sample Size:

Data Analytic Plan: The expanded population for the current amendment (N=35; patients meeting revised eligibility criteria) will be analyzed separately from the 4 patients in the original cohort.

Sample Size Considerations: A sample size of 35 patients will allow for the assessment of feasibility of delivering MAAT-G in this population⁵⁷ and also allow for thematic saturation of qualitative interviews. The effect size of MAAT-G in older adults with MCI is not known. MAAT has demonstrated a medium effect size ($d = 0.52$) on perceived cognition (FACT-Cog) in younger cancer survivors.⁵⁷ Using Repeated Measures Analysis of Variance (ANOVA) design and pre-post correlation of 0.5, and 25% attrition,⁵⁷ a sample size of n=25 evaluable patients will provide 80% power to detect an effect size of 0.52 at the significance level of 0.10. This sample size is appropriate for preliminary studies and will allow us to conduct Aim 2 analysis and evaluate distribution parameters (mean, standard deviation) of key measures of perceived and objective cognitive function to inform future studies.

Analysis Plan (Second Primary Aim): To evaluate feasibility of enrolling and delivering a videoconferencing-based intervention to older cancer survivors with MCI, we will calculate the proportion of: 1) approached patients who enrolled; 2) identified caregivers who enrolled; 3) enrolled patients who completed all 10 MAAT-G sessions on schedule [e.g. intervention adherence]; and 4) enrolled patients who completed timepoint 2 assessment [e.g. study completion]. We will consider the delivery of the telehealth-based intervention feasible if the following are met: 1) >70% of eligible patients that are approached agree to enroll; 2) >70% of identified potential caregivers agree to enroll; 3) >75% of patients complete the 10 MAAT-G sessions; and 4) >75% of patients complete the timepoint 2 assessment. This analysis on the patients enrolled from this amendment forward (e.g. analysis will only include older cancer survivors with MCI). Mean SUS score will also be calculated for all patients completing TP2 assessment. The SUS ranges 0-100; a score >68 is above average.⁶⁸

Tertiary Objective Analysis Plan: To examine the pre-post change in perceived and objective cognitive function in older cancer survivors with MCI, we will utilize repeated measures ANOVA. Because this is a preliminary analysis with a small sample size primarily focused on feasibility, our goal with the analysis of Aim 2 is to estimate key distribution parameters (mean, median, standard deviation). We will also calculate the SUS (usability) score for each individual patient. The Usability Scale ranges 0-100; a score >68 is above average.⁶¹

Secondary Aim Analysis plan:

Qualitative Analysis of transcripts from participant/caregiver interviews will be analyzed for themes on barriers and facilitators to intervention participation. Potential themes include relevance of workshop content to older adults, potential barriers to using video-conferencing technology for the target population and mechanisms for minimizing this barrier, and/or the content and formatting of participant workbook to ensure relevance and usability for older adults.

Mixed Methods Integration: Qualitative and quantitative data will be integrated to develop a more complete understanding of the usability of MAAT-G . In addition, it will enhance our understanding of

the participant experience with MAAT-G and help to explore potential benefits beyond what is captured in qualitative tools alone. Data will be organized using MAXQDA joint displays.⁷⁴

8.3. Records to be Kept:

8.3.1. Data Collection Table:

SCHEDULE OF DATA COLLECTION		
FORM	Baseline	Post-Intervention
On Study Data (Patient and caregiver demographic information and clinical data)	X	
Eligibility confirmation components: 1. UBACC 2. MOCA, MOCA-Blind, or diagnosis of MCI 3. ADL	X	
FACT-COG	X	X
Cognitive Difficulties Scale (CDS)	X	X
COWA	X	X
HVLT-R (two different versions-form 1 and form 2)	X	X
GDS	X	X
GAD-7	X	X
IADL Survey	X	X
SUS (usability measure)		X
Semi-structured interview with patient and caregiver (if enrolled)		X

8.3.2 All hardcopy research records will be stored onsite in the University of Rochester Medical Center, in locked research files at the James P. Wilmot Cancer Center. The Cancer Center is secured with electronic key cards. Offices within the Cancer Center are again secured by key and data is kept in locked file cabinets. Electronic research records are stored on the University of Rochester Medical Center's password secured and firewall protected networks. These are the same methods of security used for patient medical records. All study data will be kept for a period of 10 years after the study and all reports and publications are complete.

8.3.3 All recorded data, such as the audio-recorded interviews/transcripts and the Zoom workshop sessions will be stored on the UR Box drive to assess fidelity of intervention delivery. Within the Box drive, data will be stored in a password protected folder with access restricted to the PI and a subset of

study team members. All personal identifiers will be deleted (e.g. de-identified) from the transcriptions of the audio-recordings. Once data is uploaded to the secure server, the data will be deleted from the audio recorders.

8.3.4. All data collected for the current study will be used in post hoc analyses as appropriate, including exploratory secondary analyses with data collected as described above. Data will not be used for future studies without prior consent of the patient. The patient's individual research record will not be shared with their treating physician, unless they provide consent or the patient's treating physician is a study physician, in which case they will have access to study data as a study co-investigator. Overall study results will be presented to participants, faculty and staff at the University of Rochester Medical Center after completion of the study. Study results will be presented at professional meetings and published.

8.3.5. The study coordinator will assign a numerical study ID to each participant once they have signed the consent form. All study forms and questionnaires will use this number and the participant's first, middle, and last initials as identifiers, to ensure data integrity. Other identifying information will not exist on these forms. A complete list of study participants with study ID, name, and contact information will be maintained separately. This linkage information will only be accessible to the study coordinator, study investigators, and the individuals responsible for maintaining the database.

8.3.6. Additionally, the data can be collected and managed by the research teams at University of Rochester Medical Center using REDCap¹⁶⁷ electronic data capture tools hosted at URMC.

8.3.6a. URMC provides the following information on the **REDCap program**: "Vanderbilt University, in collaboration with a consortium of institutional partners, has developed a software toolset and workflow methodology for electronic collection and management of research and clinical trial data, called REDCap (Research Electronic Data Capture). The REDCap system is a secure, web-based application that is flexible enough to be used for a variety of types of research. It provides an intuitive interface for users to enter data and real time validation rules (with automated data type and range checks) at the time of data entry. REDCap offers easy data manipulation with audit trails and functionality for reporting, monitoring and querying patient records, as well as an automated export mechanism to common statistical packages (SPSS, SAS, Stata, R/S-Plus). Through the REDCap Consortium, Vanderbilt has disseminated REDCap for use around the world. Currently, over 240 academic and non-profit consortium partners on six continents with over 26,000 research end-users use REDCap".

8.3.56. According to the Clinical and Translational Science Institute (CTSI), REDCap is supported with the following means. "The *CTSI Informatics Core*, a unit of the *SMD Academic Information Technology (AIT) Group*, will serve as a central facilitator for data processing and management. REDCap data collection projects rely on a thorough study-specific data dictionary defined in an iterative self-documenting process by all members of the research team, with planning assistance from the *AIT-CTSI Informatics Core*. The iterative development and testing process results in a well-planned data collection strategy for individual studies".

8.3.6c. The CTSI states that regarding security, "REDCap servers are housed in a local data center at the University of Rochester and all web-based information transmission is encrypted. REDCap was developed in a manner consistent with HIPAA security requirements and is recommended to

University of Rochester researchers by the URMC Research Privacy Officer and Office for Human Subject Protection.

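### The repeated measures ANOVA of cognitive change rests on completers only; a mixed model on all enrolled patients, shown beside it, would protect against drop-out related to baseline cognition

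*Combined protocol and SAP*

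**What the plan says.** The Tertiary Objective Analysis Plan in Section 8.2 states the method for pre-post change in perceived and objective cognition: "we will utilize repeated measures ANOVA". It calls the analysis preliminary and gives its goal as estimating means, medians and standard deviations. Section 7.3, Table 3 and the data collection table in 8.3.1 show two assessments only, baseline and post-intervention (TP2).

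The Sample Size Considerations in 8.2 enrol 35 ("A sample size of 35 patients will allow for the assessment of feasibility"), assume a "pre-post correlation of 0.5, and 25% attrition", and conclude that "a sample size of n=25 evaluable patients will provide 80% power to detect an effect size of 0.52" "at the significance level of 0.10". The effect size was observed "on perceived cognition (FACT-Cog) in younger cancer survivors". The same paragraph says the parameters are meant to inform future studies.

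Section 8.1.3 covers distributional assumptions and outliers. The documents name no analysis set, missing-data method or missing-data assumption for the cognitive outcomes, and plan no comparison of completers with non-completers.

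**The concern.** With two time points, standard repeated measures ANOVA is a paired t-test and needs both scores. The power statement, built on evaluable patients, points the same way. A patient with a baseline but no TP2 score then contributes nothing to the change estimate.

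Drop-out related to cognition is plausible here. Section 4.2 says that the usability of telehealth is less well established in people with pre-existing cognitive impairment. Section 3.7d reports full adherence in four patients, none of whom had a prior diagnosis of cognitive impairment. A study that meets the plan's own TP2 completion criterion (above 75%) could still lack 8 of 35 TP2 scores, since 27/35 = 77%.

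At stake is the change estimate handed to the next trial. If it describes only those who could finish ten video sessions, it may not describe the cohort that was enrolled.

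**Working it through.** **Inputs from Section 8.2:** N = 35 enrolled, 25% attrition, 25 evaluable, r = 0.5, d = 0.52, alpha 0.10. The power sentence gives no sidedness. I take it as two-sided, following Section 8.1.2 ("all statistical tests will be performed at the two-tailed 5% level of significance", which applies unless otherwise stated).

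**Assumptions, not in the documents:** equal SDs at the two times, and the strength of the link between baseline score and drop-out (range shown). Bias and standard errors are in baseline-SD units.

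**1. The plan's own figure.** Standardised paired change = 0.52/√(2(1 − 0.5)) = 0.52. With the exact noncentral t, alpha 0.10 two-sided, 25 pairs are needed and give 81.1% power. The plan's figure reproduces as a complete-pairs calculation.

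**2. Baselines outside the change estimate.** 35 × 0.25 = 8.75, or 35 − 25 = 10 if 25 are evaluable. So about 9 to 10 of 35.

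**3. Bias of the completers' change.** Let b be the slope of post on pre. If drop-out depends only on baseline:

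bias = (b − 1) × (mean baseline of completers − mean baseline of all enrolled).

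With equal SDs, b = r = 0.5. If drop-outs score δ SD below completers at baseline, the bracket equals (number lost/35) × δ.

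| Lost of 35 | δ = 0.5 | δ = 0.8 | Share of 0.52 |
|---|---|---|---|
| 9 | −0.5 × 9/35 × 0.5 = −0.064 | −0.5 × 9/35 × 0.8 = −0.103 | 12% to 20% |
| 4 | −0.5 × 4/35 × 0.5 = −0.029 | −0.5 × 4/35 × 0.8 = −0.046 | 5% to 9% |

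The minus sign means that improvement is understated on a higher-is-better scale when low scorers leave.

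**4. Precision.** With m = 26 pairs and N = 35:
- Completers: 2(1 − r)/m = 1/26 = 0.0385.
- Mixed model: (1 − r²)/m + (1 − r)²/N = 0.75/26 + 0.25/35 = 0.0360.

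The variance ratio is 0.936, so the standard error is √0.936 = 0.967 times as large, about 3% lower. At r = 0.3 the variance ratio is 0.910.

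**5. Simulation check** (n = 35, 40,000 runs, true change 0.52, r = 0.5, 75% completing). The odds of completing were multiplied by the factor shown per SD of baseline. The mixed model has unstructured covariance and t degrees of freedom. Coverage is of a 90% interval and power is at alpha 0.10.

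| Factor | Bias, completers | Bias, mixed | Coverage, completers / mixed | Power, completers / mixed |
|---|---|---|---|---|
| 1 (none) | 0 | 0 | 90% / 91% | 82.8% / 83.9% |
| 2 | −0.08 | about 0 | 87% / 91% | 71% / 83% |
| 3 | −0.11 | about 0 | 85% / 91% | 66% / 83% |
| 5 | −0.14 | about 0 | 81% / 91% | 61% / 81% |

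A factor of 2 lowers the enrolled mean baseline by 0.16 SD relative to completers, that is δ = 0.16/0.25 = 0.64. This agrees with step 3.

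**6. Where the mixed model does not help.** When completion depended instead on the TP2 score (factors 2 and 3), completer bias was +0.08 and +0.11, and mixed-model bias was +0.12 and +0.18.

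**The case against.** The strongest case for leaving the plan alone has five parts.

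- **The mixed model is not a free cure.** A reader might infer that it removes the problem at no cost. It does so only if drop-out is explained by the observed baseline. Decline during the programme is a plausible reason to miss TP2, and step 6 shows the model doing worse in that case. In one simulated setting with slope 1 it also lost power (77.6% against 81.2%). This stands, and is why the paired result must stay.
- **Drop-out related to cognition is not enough to cause bias.** A reader might infer that the paired analysis is valid only if drop-out is unrelated to cognition. With drop-out driven by baseline, bias also requires a slope other than 1. At r = 0.7 with equal SDs the simulated bias falls to 6 to 17% of 0.52 (factors 1.5 to 5), and at slope 1 it is zero. This stands as a condition.
- **Nothing says that baselines are thrown away.** A reader might infer that a quarter of the baseline data is discarded. The plan does not restrict baseline summaries to completers; the loss is inferred, and only for the change estimate. The stated goal also includes medians, which the mixed model does not give. This stands.
- **Attrition may be lower.** In the group's earlier pilot 89% completed follow-up (Section 3.7b), and the first four patients all finished (3.7d). Neither was an MCI cohort, but the lower row of the table in step 3 is possible.
- **The effect is modest.** The standard error of the change is about 0.196, so a bias of 0.064 to 0.103 is one-third to one-half of it, and in the conservative direction for the plan's hypothesis. True, but the bias shifts the estimate that future studies will use.

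**Conclusion.** The point holds as a low-cost improvement to a tertiary analysis. The planned change estimate rests on complete pairs, the plan is silent on missing cognitive scores, and about 9 to 10 of 35 baselines would not inform the estimate at the planned attrition. Under baseline-dependent drop-out with r = 0.5 and equal SDs, improvement is understated by 0.06 to 0.10 SD (12 to 20% of 0.52) with 9 lost, or 5 to 9% with 4 lost. The 0.5 to 0.8 SD gap behind these figures is an assumption; the documents give no value. The benefit is protection against that bias. The gain in precision, about 3% of the standard error, would not justify the change alone.

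A reader might also infer that the feasibility conclusion is at risk. The documents do not support that: the criteria in Section 8.2 are enrolment, session-completion and TP2-completion proportions, and none uses the cognitive change estimate.

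**What to change.** In the Tertiary Objective Analysis Plan of Section 8.2:

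1. State the analysis set (all enrolled MCI-cohort patients with a baseline score) and the missing-data assumption (missing TP2 scores explained by the observed baseline).
2. Estimate mean change with a linear mixed model: fixed time effect, unstructured 2×2 covariance, REML and small-sample degrees of freedom. Report the confidence interval. The details matter: in the simulation, normal limits with the maximum-likelihood variance gave 11.7% type I error against 10%. A compound-symmetry fit left bias of about −0.02 or +0.04 when the post/pre SD ratio was 0.8 or 1.25.
3. Keep the paired completer analysis and the planned medians and SDs alongside.
4. Tabulate baseline scores of completers against non-completers, so that readers can judge whether drop-out tracked baseline cognition.

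The cost is a few sentences and slightly more analysis work. The software named in Section 8.1.2 (R, SPSS, SAS) fits this model, and no new data are needed. The remaining weakness is drop-out that follows the unseen TP2 score, where the model's bias can exceed that of the paired analysis; this is why both results should be reported.

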9.0 DATA SAFETY AND MONITORING

This protocol should be considered low risk as the intervention is a cognitive behavioral therapy (CBT)-based intervention. CBT- based treatments are utilized in routine clinical care for use with community dwelling older adults. This study is designed to see if MAAT, a CBT-based intervention, is feasible to deliver to older adults cancer survivors with MCI and can improve cognitive outcomes for this population..

9.1. Adverse Event Reporting Requirements:

9.1.1. Adverse events will be reported using the URCC Adverse Event form and/or as required by the Cancer Center Clinical Trials Office.

9.1.2. Adverse events will be reported in accordance with the following guidelines:

	Grade 1	Grade 2		Grade 3				Grade 4		Grade 5		
	Unexpected and Expected	Unexpected		Expect	Unexpected		Expected		Unexpect	Expect	Unexpect	Expect
		with hospit	witho ut		with hospi	witho ut	with hospit	witho ut				
Unrelated Unlikely	Not Required	Not Required	Not Required	Not Required	Not Required	Not Required	Not Required	Not Required	10 Calendar Days	Not Required	10 Calendar Days	10 Calendar Days
Possible Probable	Not Required	10 Calendar	Not Required	Not Required	10 Calendar	10 Calendar	Not Required	Not Required	24-Hour; 5	10 Calendar Days	24-Hour; 5	10 Calendar Days

Hospitalization is defined as initial hospitalization or prolongation of hospitalization for ≥ 24 hours, due to adverse event.

9.1.3. Adverse event reports will be submitted in one of the following ways:

- (1) By email: (pdf)
- (2) By mail:
- (3) By fax:

9.1.4. An unexpected adverse event is defined as any adverse experience, the specificity or severity of which is not consistent with the risk information. This is a low risk study as interventions have been shown to improve outcomes of community-dwelling older adults. To reiterate, only adverse events attributed to the behavioral intervention will be captured and reported.

9.1.5. A serious event refers to any event in which the outcome results in any of the following: death, a life-threatening adverse experience, inpatient hospitalization or prolongation of existing hospitalization, a persistent or significant disability, incapacity, or a congenital anomaly/birth defect. Important medical events that may not result in death, be life-threatening, or require hospitalization may be considered a

serious adverse drug experience when, based upon appropriate medical judgment, they may jeopardize the participant and may require medical or surgical intervention to prevent one of the outcomes listed in this definition. We anticipate that any serious events will be related to standard of care cancer treatment and not due to the MAAT-G intervention, which is designed to improve outcomes and focus on cognitive side effects of cancer treatment. To reiterate, only adverse events attributed to the behavioral intervention will be captured and reported.

9.1.6. Adverse events will be reported in accordance with institutional policies (University of Rochester, Research Subject Review Board, local IRB, URCC CCOP, CTO, and DSMB) as per their requirements.

9.2. Data Safety Monitoring:

9.2.1. All adverse events requiring reporting will be submitted to the current Project Coordinator as described in Section 9.1. Serious adverse event reports will be forwarded to the study chair and the Data Safety and Monitoring Committee (DSMC). Adverse events are entered into a protocol-specific spreadsheet.

9.2.2. Adverse event rates are monitored utilizing the spreadsheet. If a serious adverse event is reported frequently, the study chair will conduct a detailed review. The DSMC Committee Chair will be notified and will determine if further action is required.

9.2.3. The Data Safety Monitoring Committee (DSMC) will review study progress and cumulative reports of adverse events at annual meetings and as needed. An overall assessment of accrual and adverse events will enable the committee members to assess whether significant benefits or risks are occurring that would warrant study closure.

9.2.4. The URCC will notify the other sites immediately of any serious safety concerns identified by the DSMC.

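### Sections 9.1.4 and 9.1.5 restrict adverse event capture to intervention-attributed events, but the 9.1.2 table requires reports for three classes of unrelated or unlikely-related event

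*Combined protocol and SAP*

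**What the plan says.** Section 9.1.2 introduces a table of reporting requirements by grade, expectedness, hospitalization and attribution, and presents it as the rule: "Adverse events will be reported in accordance with the following guidelines". One of its two attribution rows is labelled "Unrelated Unlikely". Most cells in that row need no report, but three carry a deadline of 10 calendar days.

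Section 9.1.4 then states: "To reiterate, only adverse events attributed to the behavioral intervention will be captured and reported". The same sentence closes section 9.1.5, after a remark that serious events are expected to come from standard cancer treatment and not from MAAT-G.

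The monitoring text depends on whichever rule applies. Section 9.2.1 says: "All adverse events requiring reporting will be submitted to the current Project Coordinator as described in Section 9.1". It also sends serious event reports to the study chair and the DSMC and has adverse events entered in a spreadsheet. Section 9.2.2 adds: "Adverse event rates are monitored utilizing the spreadsheet". Under section 9.2.3 the DSMC reviews cumulative reports at least annually and considers whether the study should close.

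Two further routes are named without detail. Section 9.1.1 refers to reporting "as required by the Cancer Center Clinical Trials Office", and section 9.1.6 says: "Adverse events will be reported in accordance with institutional policies".

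**The concern.** The table requires reports on some events that the text says will be neither captured nor reported. A coordinator facing a death judged unrelated to MAAT-G finds a 10-day deadline in one place and an instruction not to record it in another.

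The restriction applies to capture, not only to onward reporting. An event set aside at the first attribution judgement leaves no study record from which that judgement could be checked later. There is no randomization (section 6.3), so no comparison arm could reveal a pattern of misattributed events. Section 9.1.5 itself expects serious events to be unrelated to the intervention, which puts them in the row where the two rules collide. Participants are 65 or older with a prior cancer of any stage (section 4.1) and are in the study for up to 8 months (section 5.1.6), so such events are plausible, although the protocol gives no expected number.

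**Working it through.** The protocol states no numerical figure to reproduce on this point. The check is a reading of the 9.1.2 table against the text.

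**Step 1: columns.** The table is broken in the extracted text, so the layout is inferred. The header lines giving expectedness and hospitalization imply:

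- Grade 1: 1 column
- Grade 2: 3 (unexpected with and without hospitalization; expected)
- Grade 3: 4 (unexpected with and without; expected with and without)
- Grade 4: 2 (unexpected; expected)
- Grade 5: 2 (unexpected; expected)

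Total: 1 + 3 + 4 + 2 + 2 = 12. Each attribution row has exactly 12 entries, so the cells align.

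**Step 2: cells requiring a report.**

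| Column group | Unrelated or unlikely | Possible or probable |
|---|---|---|
| Grade 1 | 0 of 1 | 0 of 1 |
| Grade 2 | 0 of 3 | 1 of 3 (unexpected, with hospitalization) |
| Grade 3 | 0 of 4 | 2 of 4 (unexpected, with and without hospitalization) |
| Grade 4 | 1 of 2 (unexpected) | 2 of 2 |
| Grade 5 | 2 of 2 | 2 of 2 |
| Total | 3 of 12 | 7 of 12 |

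Across both rows: 3 + 7 = 10 of 24.

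**Step 3: apply the text.** No reasonable reading makes an event in the first row one that is attributed to the intervention.

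| Event judged unrelated or unlikely | Table in 9.1.2 | Text in 9.1.4 and 9.1.5 |
|---|---|---|
| Unexpected Grade 4 | report in 10 calendar days | not captured or reported |
| Unexpected Grade 5 | report in 10 calendar days | not captured or reported |
| Expected Grade 5 | report in 10 calendar days | not captured or reported |

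The text contradicts 3 of the 10 cells that require a report, and 2 of the 4 Grade 5 cells, all 4 of which require one. The other 9 cells of the first row (12 − 3 = 9), including expected Grade 4, need no report, so the two rules do not collide on reporting there.

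**Step 4: does the monitoring section settle it?** No. Section 9.2.1 defines what is submitted by pointing back to section 9.1, which holds both rules. The spreadsheet, the rates computed from it and the DSMC's cumulative review inherit the conflict.

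**The case against.** The strongest reply is that the consequence turns on policies that are not shown. Sections 9.1.1 and 9.1.6 bind the study to the requirements of the Clinical Trials Office, the review board and others. If those require unrelated deaths to be reported, staff must report them whatever section 9.1.4 says. This stands in part: a conflict of wording is proven, lost events are not. But neither section says which rule prevails, and policies whose content is not given cannot be assumed to resolve it.

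Second, this is a small single-arm feasibility study, with 35 patients in the cohort with mild cognitive impairment, of a behavioral program that the protocol calls low risk. That could justify a narrow reporting rule. It does not justify two incompatible ones.

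Third, the contradiction does not show which rule was intended. The restricting sentence appears twice, section 9.1.5 gives a reason for it, and editing three table cells would also remove the conflict. This is fair, and the essential request is one consistent rule.

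Fourth, the cell counts describe the table, not patients or events, and the 3 of 10 assumes that attributed events are exactly those in the possible or probable row. The protocol does not define the term; a stricter meaning would widen the conflict. Both points are correct and limit what the ratios can show.

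**Conclusion.** The concern holds. For unexpected Grade 4 events and all Grade 5 events judged unrelated or unlikely to be related, the table and the text cannot both be followed. The conflict covers 3 of the 12 cells in that row and 3 of the 10 cells in the whole table that require a report. If staff apply sections 9.1.4 and 9.1.5 literally, these events could be missing from the spreadsheet and not reach the DSMC.

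This rests on the column layout inferred above, on Grade 5 meaning death (the protocol does not spell out its grading scale), and on institutional policies not closing the gap. How many participants would be affected cannot be estimated from the documents. The sample size, feasibility criteria and cognitive analyses do not change. The point is an internal inconsistency in safety reporting that should be corrected.

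**What to change.** Reconcile sections 9.1.2, 9.1.4 and 9.1.5 so that one rule governs. The most direct way is to delete the restricting sentence in both places and state instead that every event for which the 9.1.2 table requires a report is captured and reported regardless of attribution, with the attribution recorded on the report. This keeps the table as written and gives section 9.2.1 a single rule to refer to. If the sponsor did intend the narrower rule, the three table cells would have to change instead, with the reason given.

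The cost is a wording change in two places and probably a few more entries, using the adverse event form named in section 9.1.1 and the spreadsheet named in section 9.2.1.
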